A phase I clinical study of intravenous administration of Nemonoxacin malate sodium chloride injection was carried out in China and consisted of four parts (TG-873870-C-2: part A, B, C-1 and C-2). During the part A of study the tolerability of intravenous Nemonoxacin malate injection was investigated. To explore the safe dose by evaluating the safety and tolerability of eight dose levels of nemonoxacin (25, 50, 125, 250, 500, 750, 1000 and 1250 mg) the drug was given as single intravenous dose in Chinese healthy subjects. A total of 92 subjects were assigned into 12 groups with equal numbers of male and female. The tolerated-dose study of the nemonoxacin indicated that the tolerated-dose ranged from 25 mg to 1250 mg and the maximum dose was 1250 mg. The most common drug-related AE was local reaction at administration sites (27/68) and skin rash with or without pruritus (13/68) All AEs were mild and transient, and recovered spontaneously during the administration or shortly after administration. No important or serious AEs that led to study discontinuation and clinical significant change in ECG was observed. As for the laboratory tests, no drug related hyperglycemia or hypoglycemia occurred. The infusion rate of the drug ranged from 0.42 mg/min to 8.33mg/min. The occurrence of skin rash was more common with infusion rate of 8.33 mg/min (3 subjects each in 500 mg and 750 mg group), and all other infusion rates (0.42 mg/min to 5.56 mg/min) were tolerated well.

Part B of the trial evaluated the pharmacokinetic profiles of single-dose nemonoxacin malate sodium chloride injection at 250, 500, and 750mg in healthy Chinese volunteers (see Brochure for details).

During the part C-1 (500 mg and 750 mg doses were investigated) and C-2 (500 mg, 650 mg and 750 mg doses were investigated) of study the tolerability and pharmacokinetics of the multidose continuous intravenous infusion of nemonoxacin malate was investigated. During these studies there were no serious AEs and clinical significant change in ECG. In the C-1 study after the multiple intravenous infusions of nemonoxacin C_{max} on day 10 (steady state) in the 500mg and 750mg group was $9.600\pm1.838~\mu g/mL$ and $11.039\pm2.177~\mu g/mL$ respectively. AUC $_{0-t}$ (for 500 mg group: 22.5h; for 750 mg group: 21.75h) was $44.03\pm8.62~\mu g.h/mL$ and $65.82\pm10.78~\mu g.h/mL$ respectively. Statistical analysis revealed no cumulative effect in both groups after administration for consecutive 10~days [28].

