3.3.2.2 Phase II clinical trials

A randomized, double-blind, comparative, multi-center study (#TG-873870-02) of the safety and efficacy of oral nemonoxacin versus oral levofloxacin in adult patients with CAP was carried out in 19 study centers in South Africa and Taiwan. A total of 265 subjects were enrolled and randomized in the study: 86 patients in the nemonoxacin 750 mg group, 89 in the nemonoxacin 500 mg group and 90 in the levofloxacin 500 mg group. Patients received therapy once daily for 7 days. The study revealed that 750 and 500 mg nemonoxacin had similar clinical efficacy when compared with 500 mg levofloxacin once daily for 7 days. The safety profile of nemonoxacin was also similar to that of levofloxacin and it was consistent with the favorable safety results of nemonoxacin in previous phase I studies [28].

Efficacy and safety of Nemonoxacin malate sodium chloride injection versus Moxifloxacin hydrochloride sodium chloride injection in the treatment of moderate to severe adult CAP were evaluated during a multi-center, randomized, double-blind, parallel, controlled, phase II study. Patients received either 500 mg nemonoxacin, 650 mg nemonoxacin, or comparator drug moxifloxacin 400 mg once a day for 7 to 14 days. A total of 207 subjects were randomly enrolled in 30 research centers: 69 subjects were in the nemonoxacin 500mg group, 68 subjects were in the nemonoxacin 650 mg group and 70 subjects were in the control group (moxifloxacin 400mg). Nemonoxacin had shown similar clinical efficacy, microbiological efficacy, and overall efficacy when compared with moxifloxacin hydrochloride sodium chloride injection once a day for 7 to 14 days. The AEs reported during the study were mostly mild, transient, and tolerated by most patients. The main drug-related AEs in patients who received nemonoxacin were local reactions at the infusion site. The main drug-related laboratory abnormalities were elevated liver transaminases without bilirubin elevation [24].

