7.3 Discontinuation of Therapy and Withdrawal of the Patients from the Study

Study therapy should be discontinued and the patient should be withdrawn from the study due to any of the following reasons:

- Informed consent withdrawal (the patient has made the decision to stop the participation in study for any reason)
- The patients require other antibiotic treatment
- Development of any adverse event, including serious adverse event, clinical significant deviation in the laboratory results, or concomitant disease, which at the investigator's opinion indicates, that continuation of the study medication administration is not at the patient's best interest
- Pregnancy
- Termination of the study by the Sponsor (e.g. in case of poor safety results)
- Termination of the study by the Regulatory Authority (e.g. in case of poor safety results).

CONFIDENTIAL Page 36 of 88

In all cases the reason of termination of participation in study must be recorded in eCRF. When the patient is withdrawn from the study, all efforts should be made to perform all procedures scheduled for the "early termination visit":

- if the "early termination visit" coincides in time with scheduled visit the procedures of that visit should be done (Section 9.2);
- if the "early termination visit" coincides in time with unscheduled visit the minimum number of procedures should comply with the "End of treatment visit" (Section 9.2.3).

All the patients withdrawn from the study will receive treatment in accordance with the standards adopted in the hospital.

Withdrawn patients will not be replaced.

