11.2 Monitoring and Recording of Adverse Events

At each visit during the study period the Investigator will assess and record in the eCRF any subjective or objective:

- AEs occurred after the first IMP administration on Day 1 of Visit 1 and up to the moment of last procedure at Visit 5
- SAEs occurred after the obtainment of the informed consent (after the signing of ICF) on Day 1 of Visit 1 and up to the moment of last procedure at Visit 5.

AEs communicated by the patient or by the patient's relatives or delegates through phone calls, letters or E-mails will also be recorded. In these cases the Investigator will try to obtain medical confirmation and assessment of the occurred AE.

When an AE has occurred the Investigator will record on the respective electronic Case Report Form Adverse Event (eCRF-AE) recording pages any case, Serious and Non-Serious, whether or not thought to be drug-related, observed in or reported by the patient (or relatives/delegates), specifying the judgement on the causal relationship with the study treatment.

Any available information and diagnostic measure (laboratory and instrumental tests, procedures etc.), will be recorded in the eCRF.

The Investigator is expected to follow-up any AEs occurred during the Study until the resolution of the event or permanent outcome has been determined.

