12 STATISTICAL METHODS

12.1 Analysis populations

The following populations will be identified for the statistical analyses:

- Randomized Population (RP): All subjects who were screened and randomized
- Intent-to-Treat Population (ITT): All subjects in the RT population who received at least one complete dose of the drug (Nemonoxacin or Tavanic[®])
- Modified Intent-to-Treat (mITT): Subjects in the ITT population who met the minimal disease criteria (inclusion criteria 3 and 4), and was evaluated for clinical efficacy at least once
- Clinically Evaluable (CE): Per-Protocol subjects in the mITT population (i.e. patients without protocol violations and without a clinical response of "Indeterminate" in the mITT population)
- Bacteriological mITT (b-mITT): Subjects in the mITT population whose bacterial culture yielded at least one baseline bacterial isolate
- Bacteriologically Evaluable (BE): patients in the CE population who had at least one baseline bacterial isolate
- Safety Population (SP): All subjects who received at least one complete dose of the study drug (Nemonoxacin or Tavanic®) and underwent at least one safety evaluation would be included in this data population for safety analysis
- Pharmacokinetic population (PK-C): All subjects who were included in PK study and who had at least 1 measured concentration value.

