12.7 Safety evaluation

Safety evaluation will include assessment of AEs, vital signs, ECG, physical examination data and laboratory assessment in the safety population. All safety statistical analyses will be performed descriptively.

AEs/ADRs/SAEs will be analyzed descriptively, the evaluation of adverse events will comprise various frequency tabulations by system organ class and preferred term coded according to MedDRA. The AEs will be will be tabulated for each treatment group separately on a patient basis (counting each preferred term once per patient). Descriptive statistics will be also tabulated by relation to study drugs and severity by treatment group. The tables for AEs will present the number of patients with an event within each preferred term as a percentage of the number of treated patients. The number of events within each preferred term will also be reported. For each patient and each adverse event, the worst severity category recorded will be used in the by-severity summaries. The worst causality category (most related to treatment) will be used in the by-causality summaries.

Blood count, biochemistry and urinalysis data as well as change from baseline in laboratory data will be tabulated descriptively by treatment group and by visit. Frequency tables of laboratory shifts with respect to the reference range will also be presented. Clinically relevant abnormalities will be listed individually.

Vital signs data and change from baseline values will be summarized descriptively by treatment group and by visit.

The baseline and postbaseline ECG as well as physical examination data will be summarized descriptively by visit and by treatment group.

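### Requiring one complete dose for the Safety Population and ITT drops patients whose infusion was started and stopped for good, so their adverse events reach no safety table

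*Combined protocol and SAP*

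**What the plan says.** Section 12.1 defines the Safety Population as "All subjects who received at least one complete dose of the study drug" (Nemonoxacin or Tavanic) with at least one safety evaluation. ITT is defined as "All subjects in the RT population who received at least one complete dose of the drug". The mITT set, used for the primary analysis, is a subset of ITT; CE, b-mITT and BE lie inside mITT. No section defines a complete dose. The nearest text is the compliance rule in 12.2, which counts an incomplete intravenous infusion regimen as one missed dose; it is not applied to the populations.

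Other sections work from first exposure or from treatment:

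- Section 11.2 collects "AEs occurred after the first IMP administration on Day 1 of Visit 1", with no condition on completing the dose.
- Section 12.7 states: "Safety evaluation will include assessment of AEs, vital signs, ECG, physical examination data and laboratory assessment in the safety population".
- The same section gives adverse event counts "as a percentage of the number of treated patients".
- Section 7.3 links stopping to withdrawal: "Study therapy should be discontinued and the patient should be withdrawn from the study due to any of the following reasons". One listed reason is an adverse event after which the investigator judges continuing not to be in the patient's interest.

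**The concern.** A safety set should contain everyone exposed. This one leaves out patients who were exposed, stopped before finishing a dose and never received a full one. Intolerance of the infusion is the main way this could happen, and for the intravenous product section 3.3.2.2 reports: "The main drug-related AEs in patients who received nemonoxacin were local reactions at the infusion site". Reactions that do not stop the infusion, and reactions to later doses, are still counted; what is lost is the event that ended treatment before one full dose.

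For efficacy, mITT inherits a condition that is met or failed after randomization and that, on one reading, differs by arm.

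**Working it through.** **1. Can an exposed patient stay out for good?** A stopped infusion alone does not exclude anyone, because a later complete dose restores the patient. If an adverse event ends therapy during the first infusion, however, 7.3 also withdraws the patient and no later dose follows. Sections 7.3 and 9.3 ask for an early termination visit; if unscheduled, it has at least the end-of-treatment procedures, which under 9.2.3 include vital signs, ECG, laboratory tests and a clinical response assessment. Such a patient can therefore have both a safety and an efficacy evaluation, and the complete-dose clause alone can be what removes them.

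**2. Does the rule act alike in both arms?** Under 6.1 the 250 ml bag (90–110 min) always precedes the 100 ml bag (at least 60 min). The first bag is active in the nemonoxacin arm and placebo in the Tavanic arm. For a patient who gets no later dose:

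| Infusion stopped during | Nemonoxacin arm | Tavanic arm |
|---|---|---|
| Bag 1, complete dose = active bag | out, partly exposed to active drug | out, placebo only |
| Bag 2, complete dose = active bag | **in** | **out**, partly exposed to active drug |
| Either bag, complete dose = both bags | out | out |

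On the active-bag reading, the Day 1 time during which a stop means exclusion is 90–110 min for nemonoxacin and at least 150–170 min for Tavanic (150/90 = 1.67; 170/110 = 1.55). On the two-bag reading the rule is symmetric, but it also drops nemonoxacin patients who received the whole active bag.

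**3. How many patients?** The documents give no rate. This trial infuses at 500/110 = 4.55 to 500/90 = 5.56 mg/min. Section 3.3.2.1 says "all other infusion rates (0.42 mg/min to 5.56 mg/min) were tolerated well", which suggests few. Assuming a proportion p never completes a dose, with 171 per arm:

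| p | Expected per arm, 171p | Chance of at least one, 1 − (1 − p)^171 |
|---|---|---|
| 0.5% | 0.9 | 58% |
| 1% | 1.7 | 82% |
| 3% | 5.1 | 99% |

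**4. Effect on a safety table.** If k such patients each had an event, the as-treated figure is k/171 and the planned table shows 0/(171 − k). For k = 1 this is 0.58% against 0/170; for k = 5, 2.92% against 0/166.

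**5. Effect on the primary comparison.** Section 12.10 assumes 82% success and about 137 per arm in mITT: 0.82 × 137 = 112.3, so take 112/137. One-sided 95% Farrington-Manning lower limits (score test with restricted maximum likelihood estimates), nemonoxacin minus Tavanic, with the restored patients counted as failures:

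| Scenario | Nemonoxacin | Tavanic | Difference (points) | Lower limit (points) |
|---|---|---|---|---|
| None restored | 112/137 | 112/137 | 0 | -7.74 |
| 4 to nemonoxacin only | 112/141 | 112/137 | -2.32 | -10.15 |
| 4 to Tavanic only | 112/137 | 112/141 | +2.32 | -5.54 |
| 2 to each | 112/139 | 112/139 | 0 | -7.86 |
| 5 to each | 112/142 | 112/142 | 0 | -8.00 |

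All stay above -15. Some of these patients would remain outside mITT anyway for lack of an efficacy evaluation.

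**The case against.** - **The arm difference depends on the reading.** Section 6.1 describes daily therapy as two consecutive infusions and 12.2 speaks of the infusion regimen, so the two-bag reading is reasonable. This stands, and the arm difference is claimed only for the literal reading. Choosing the two-bag reading does not help safety, because it excludes more exposed patients.
- **The events are not lost.** They remain in the eCRF, and serious events are still reported within 24 hours. This stands; the loss is from the analysis tables. Section 12.2 keeps patients with deviations in the safety analysis, but only within the Safety Population of 12.1. The treated-patients denominator in 12.7 points the other way, but that is a conflict inside the plan and does not repair it.
- **Few patients are involved.** In the phase I intravenous study (3.3.2.1) local reactions (27/68) and rash (13/68) were common, but events were mild and transient and no important or serious event led to discontinuation. Consent withdrawal and other reasons in 7.3 can also end treatment early. This stands and limits the size of the problem.
- **The SAP may settle it.** Section 12.9 promises more detail there, and 12.5 defers missing, unused and spurious data. Neither says that the population definitions will change, and the definition given in 12.1 is explicit.

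**Conclusion.** The concern holds. Followed as written, the plan removes from its safety analysis any patient who was exposed but never completed a dose, and it leaves open what a complete dose is. The number is probably small: about 1 to 5 per arm if 0.5% to 3% of patients are affected, a range that is assumed and has no source in the documents. No efficacy scenario examined crosses the -15 point margin, and the net direction of any bias is unknown. The rule should be corrected because it gives the wrong safety set, not because it threatens the primary conclusion.

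**What to change.** - **Safety Population:** all patients in whom any volume of either blinded infusion was started. Drop the condition of a later safety evaluation, since it could exclude the same early stoppers.
- **Section 12.7:** state that the treated-patients denominator is this set.
- **ITT:** all randomized patients, or all randomized patients in whom any blinded infusion was started. Either applies alike in both arms and frees mITT from the complete-dose condition. The first also admits patients never dosed, so the choice must be stated.
- **Section 12.2:** if complete dose is kept for compliance, say whether it means the active bag or both bags.

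The separate mITT requirement of at least one efficacy evaluation is left as it is.

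The cost is two definitions and two clarifying statements; 8.9 already records the volume and the start and stop times of each infusion. There are three drawbacks. A Tavanic-arm patient stopped in bag 1 enters the safety set having received only placebo; a listing by volume and bag would show this. Success rates may fall slightly. Early stoppers who reach mITT without a Visit 4 outcome will need the missing-data rule that 12.5 leaves to the SAP.

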12.2 Exclusion of Patients from Analysis

The investigator should not implement any deviation, except where necessary to eliminate an immediate hazard to the patient.

Data obtained from patients with protocol violations/deviations will be included into the efficacy analysis of the modified Intent-to-Treat (mITT) and bacteriological mITT (b-mITT) populations and the safety analysis (safety population, SP) (see Section 12.1). Data obtained from patients with protocol violations and major deviation will not be included into the efficacy analysis of the clinically evaluable (CE) and bacteriologically evaluable (BE) populations (see Section 12.1); however, data obtained from patients with minor deviations may be included into the efficacy analysis of the CE and BE population.

CONFIDENTIAL Page 63 of 88

Any protocol deviations should be documented in the eCRF.

A protocol deviation is any change, divergence, or departure from the study design or procedures of a protocol that is under the investigator's control and that has not been approved by the IEC. Protocol deviations do not interfere with or may not influence significantly the trustworthiness of the obtained data and the results of the clinical study. There are major and minor protocol deviations. Major protocol deviations may lead to quality depreciation of the data for the following analysis (e.g., intake of prohibited medication, skipping TOC visit, etc.). Minor protocol deviations may decrease the data quality, but it is possible to include them in the analysis in CE and BE population (e.g., partial performance of some study procedures, etc.).

A protocol violation is a deviation from the IEC approved protocol that may affect the subject's rights, safety, or well-being and/or the completeness, accuracy and reliability of the study data. The protocol deviation should be referred to violation in the following cases:

- enrollment of patients not eligible according to the inclusion/exclusion criteria,
- enrollment of patients after the Sponsor's announcement about the enrollment termination,
- Poor compliance:
 - Patient took IMPs <80% or >120% predefined total dose (any incomplete intravenous infusion regimen will be recorded as missing 1 dose of drug), or
 - The patient took IMPs <7 days
- Patients who received the treatment different from the one they were randomized to,
- Other deviations that might affect the primary outcome assessment.

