8.7.2 Prohibited and limited in use therapy

During treatment period (from Visit 1 to Visit 3) the following medications should be prohibited:

- 1. Antacids, multivitamins containing calcium, magnesium, iron, zinc, or aluminum, and sucralfate should be prohibited within 3 hours before and after oral administration of the investigational drug. Intravenous therapy should not be coadministered with any solution containing multivalent cations, e.g., magnesium, through the same intravenous line.
- 2. Probenecid.

During study period (from Visit 1 to Visit 5) the following medications should be prohibited:

- 1. Drugs that may prolong the QT interval with known risk or possible risk of Torsades de Pointes (TdP). The list of these drugs is presented in Appendix 3.
- 2. Chemotherapeutic agents or antitumor drugs.
- 3. Other systemic antibacterial drugs (except for treatment failure).
- 4. Systemic immunosuppressive drugs, including inhaled steroids.
- 5. Drugs that may act to alter the signs and symptoms of infections (e.g., antipyretics, analgesics, antihistamines, or cough suppressants) since day 3 (including) of the treatment.
- 6. Investigational products other than studied in this trial and other than the patient has been randomized.

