12.6.3 Secondary efficacy analyses

As a supportive analysis, the primary efficacy endpoint will be analyzed in the CE population using the same method as that used for the primary efficacy analysis.

For secondary efficacy analyses, the clinical success rates of the patients in the mITT and CE populations at Visit 2 (switch to oral therapy) and Visit 3 as well as the number (proportion) of patients who needed other antibiotic treatment (treatment failure) will be analyzed using a two-sided 95% confidence interval (equality test) calculated based on the same statistical test as for the primary analysis.

Additionally, the results of statistical comparison of the clinical success rates using the logistic regression will also be provided.

Time to switch therapy from i.v. to oral therapy will be evaluated using the Kaplan – Meier survival analysis method and compared by log-rank test between treatment groups. The Kaplan-Meier curves will be presented graphically.

Microbiological efficacy endpoints will include microbiological success rates evaluated per each patient and by identified pathogens in b-mITT and BE.

The percentage and the number of patients with microbiological success and failure will be summarized by visit and treatment group. Microbiological success is defined as the assessments of eradication and presumed eradication. Other results of assessments (excluding unevaluable) will be regarded as microbiological failure. The difference between microbiological success rates and its CI will be calculated using the same method as that used for the secondary efficacy endpoints.

The percentage and number of the baseline-identified strains (sputum and blood culture) with microbiological success and failure will be summarized by visit and treatment group. The frequency of each category and sample source (sputum and blood culture) will be presented separately and by treatment group. Microbiological data by identified pathogens will be analyzed descriptively.

Microbiological efficacy evaluation

Based on the results of culture (bacteriological) study the microbiological response will be assessed. Microbiological response is defined as:

- 1. Eradication (admission pathogen[s] is absent),
- 2. Presumed eradication (if no material available for culture because of clinical success)
- 3. Persistence (admission pathogen[s] is present),
- 4. Presumed persistence (no material available for culture for patients with clinical failure),

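### Sections 12.1 and 12.2 define CE differently, and the prohibited-medication exclusion in 12.2 has no time limit, so read literally it drops patients for a drug taken after the primary outcome is recorded

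*Combined protocol and SAP*

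**What the plan says.** **CE in 12.1.** CE consists of mITT "patients without protocol violations and without a clinical response of" Indeterminate. Major deviations are not mentioned. BE is the part of CE with a baseline isolate, so it inherits whatever rule CE has.

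**CE in 12.2.** This section goes further: "Data obtained from patients with protocol violations and major deviation will not be included into the efficacy analysis of the clinically evaluable (CE") and BE populations. It separates violations, which it lists, from major deviations, for which it gives examples: "Major protocol deviations may lead to quality depreciation of the data for the following analysis (e.g., intake of prohibited medication, skipping TOC visit, etc". Intake of prohibited medication is not an item in the violation list, although that list closes with a general item for any other deviation that could influence the primary assessment. The same section keeps all deviators in mITT.

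**What is prohibited, and until when.** Section 8.7.2 states: "During study period (from Visit 1 to Visit 5) the following medications should be prohibited". Among the items are: "Drugs that may act to alter the signs and symptoms of infections (e.g., antipyretics, analgesics, antihistamines, or cough suppressants) since day 3" of treatment. Antibacterials given for treatment failure are exempt. Symptomatic drugs have no such exemption.

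**Timing.** The primary outcome is set at Visit 4, 7-9 days after the last dose (9.2.4). Visit 5 is a telephone contact 21-23 days after the last dose (9.2.5).

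**Role of CE.** Section 12.6.3 says that "the primary efficacy endpoint will be analyzed in the CE population using the same method" as the primary analysis, as support for it. Section 12.6.2 makes mITT the primary population.

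**The concern.** Two sections that should produce one list of patients can produce two. A programmer following 12.1 would keep a patient whose only departure was a prohibited medicine; one following 12.2 would remove that patient. If the choice is left until after the data are in, CE membership becomes a matter of judgement.

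The 12.2 rule also has no end date of its own. It borrows the 8.7.2 window, which runs well past the primary assessment. A patient with a recorded Visit 4 outcome can then leave CE because of a later analgesic that had no way of influencing that outcome.

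Before Visit 4 there is a further issue. Table 10-1 defines clinical failure partly by symptoms that persist or worsen, and the prohibited drugs treat such symptoms. If failures take them more often than successes do, the exclusion removes failures preferentially. Success rates in both arms then rise and a real deficit shrinks, even when drug use is the same in the two arms. In a non-inferiority trial that would make the supportive analysis agree with a favourable conclusion too readily.

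**Working it through.** **1. Length of the post-outcome window.** Shortest gap between Visits 4 and 5: 21 - 9 = 12 days. Longest: 23 - 7 = 16 days. Read literally, one dose of a listed symptomatic drug in that period is a major deviation under 12.2.

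**2. Where 12.1 and 12.2 disagree.**
- *Use between Day 3 and Visit 4.* 12.2 removes the patient. 12.1 probably does too, through the general last item of the violation list, because a symptom-altering drug could influence the assessment.
- *Use after Visit 4.* 12.2, read literally, removes the patient. 12.1 keeps the patient, because a later drug cannot influence a completed assessment and the general item is not met.

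The clear disagreement is therefore the post-Visit 4 case.

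**3. Inputs for the size.** From section 12.10: 82% success, a 15-point margin, one-sided 5%, and 80% of 171 randomized per arm in mITT. The arm size checks: 0.80 × 171 = 136.8, about 137. (The stated success rate, margin, alpha and 80% power give about 82 to 84 per arm, not 137. That is a separate matter; 137 serves here only as the planned arm size.) The documents give no rate of prohibited-drug use, so every rate below is an assumption.

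**4. Precision.** Half-width of the one-sided 95% limit = 1.645 × √(2 × 0.82 × 0.18 / n).
- n = 137: 7.6 points.
- If 20% are removed regardless of outcome, 0.80 × 137 is about 110, giving 8.5 points.

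No bias arises in this case.

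**5. Possible outcome-related loss before Visit 4.** Let rs and rf be the shares of successes and failures removed, the same in both arms. Then

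CE success = p(1 - rs) / [p(1 - rs) + (1 - p)(1 - rf)].

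Take a true 82% against 67%, exactly at the margin.

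| rs | rf | Comparator in CE | Nemonoxacin in CE | Difference (points) |
|---|---|---|---|---|
| 15% | 15% | 82.0% | 67.0% | -15.0 |
| 2% | 5% | 82.5% | 67.7% | -14.8 |
| 2% | 10% | 83.2% | 68.9% | -14.4 |
| 5% | 10% | 82.8% | 68.2% | -14.6 |
| 5% | 15% | 83.6% | 69.4% | -14.2 |
| 15% | 30% | 84.7% | 71.1% | -13.5 |
| 15% | 50% | 88.6% | 77.5% | -11.0 |

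Worked example, last row. Comparator: 0.82 × 0.85 = 0.697 and 0.18 × 0.50 = 0.090, so 0.697 / 0.787 = 88.6%. Nemonoxacin: 0.67 × 0.85 = 0.5695 and 0.33 × 0.50 = 0.165, so 0.5695 / 0.7345 = 77.5%.

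Starting from 137 per arm, the normal-approximation chance that CE shows non-inferiority at this true margin is 5% with equal use, about 8% in the 15%/30% row and about 19% in the 15%/50% row.

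**6. Effect of keeping every failure.** Suppose failures stay in CE whatever they took (rf = 0) while 15% of successes are still removed. Comparator: 0.697 / (0.697 + 0.18) = 79.5%. Nemonoxacin: 0.5695 / (0.5695 + 0.33) = 63.3%. The difference is -16.2, a distortion in the other direction.

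**The case against.** **Post-Visit 4 removal may not be intended.** Section 12.2 limits deviations to departures that the investigator can control, and describes major ones as liable to degrade the data for analysis. A drug taken at home after discharge fits neither description well. This stands in part: removal is the literal reading of the named example, not a certain one. That ambiguity is itself a reason to state a window.

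**A reader might infer that CE is bound to lose failing patients.** The documents do not support that. They give no rates of use. Patients stay in hospital during treatment, under staff who are told not to allow these drugs from Day 3, so use on treatment may be rare. Rescue antibacterials are exempt, and patients needing another antibiotic are withdrawn under 7.3. With low use the distortion is under one point. Outcome-related loss is a reasonable possibility, no more.

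**A reader might also infer that the two sections conflict for every user of a prohibited drug.** The general violation item probably brings most use before Visit 4 under 12.1 as well.

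**Excluding users of symptom-altering drugs is a normal per-protocol aim.** Such drugs can mask failure. This stands, and is why the main CE rule should continue to exclude use before Visit 4.

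**Detail is deferred.** Section 12.9 leaves analysis detail to an SAP finalized before database close-out, and the documents contain no separate SAP text. The classification may be settled there, but the two protocol sections still need to agree.

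**Conclusion.** The inconsistency between 12.1 and 12.2 is real, and so is the missing time limit. Read literally, 12.2 discards settled primary outcomes because of events in the following 12-16 days. The cost is precision: if 20% were lost regardless of outcome, the half-width would grow from 7.6 to 8.5 points.

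Bias from use before Visit 4 is conditional. It needs failures to take these drugs more often than successes, and its size rests wholly on assumed rates: none with equal use, 0.2 to 0.8 points with low use, 4 points at the heaviest use shown. If failures took them less often, the bias would reverse.

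It would be wrong to conclude that the trial's main result is compromised. Non-inferiority is decided in mITT, which keeps these patients, and no text requires CE to succeed. The point concerns the supportive CE analysis and the microbiological analyses in BE.

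**What to change.** Leave the clinical ban in 8.7.2 unchanged and amend only the analysis rule.

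1. State in both 12.1 and 12.2 that CE excludes protocol violations, major deviations and Indeterminate responses. BE follows from CE.
2. State in both that prohibited medication counts as a major deviation for CE only if taken before the Visit 4 assessment.
3. Add a CE sensitivity analysis in which patients who met the Table 10-1 failure criteria at or before Visit 4 are kept as failures regardless of symptomatic medication. Say plainly that it leans against non-inferiority, because successes who took the same drugs are still removed (for example -16.2 for a true -15 if 15% of successes are removed). Read beside the main CE result, it shows how much the exclusion matters.

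The cost is wording in two sections and one extra analysis, with no change to data collection. It should be settled before database close-out, so that CE membership is not decided case by case.
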